Patient Group	Optum	MarketScan	Medicare
Overall Patient Population	127 [58-306]	149 [72-341]	147 [81-318]

Referent	121 [58-297]	153 [87-327]	153 [87-327]
Exposure	134 [58-318]	142 [58-310]	142 [58-310]

- For canagliflozin vs. 2nd generation SUs

Median Follow-Up Time (Days) [IQR]			
Patient Group	Optum	Marketscan	Medicare
Overall Patient Population	141 [63-336]	159 [83-358]	172 [90-373]
Referent	140 [75-330]	200 [118-414]	200 [118-414]
Exposure	141 [58-341]	144 [62-327]	144 [62-327]

- Report risk per 1,000 patients

Action report name:

- For canagliflozin vs. DPP4i

Optum- <https://bwh-dope.aetion.com/#/projects/details/660/results/34590/result/0>

Marketscan- <https://bwh-dope.aetion.com/#/projects/details/661/results/34591/result/0>

Medicare- <https://bwh-dope.aetion.com/#/projects/details/662/results/34592/result/0>

- For canagliflozin vs. 2nd generation SUs

Optum- <https://bwh-dope.aetion.com/#/projects/details/660/results/34596/result/0>

Marketscan- <https://bwh-dope.aetion.com/#/projects/details/661/results/34597/result/0>

Medicare- <https://bwh-dope.aetion.com/#/projects/details/662/results/34598/result/0>

Date conducted: 04/25/2019

For canagliflozin vs. DPP4i

	Optum	Marketscan	Medicare
Risk per 1,000 patients	7.58	7.81	22.56

For canagliflozin vs. 2nd generation SUs

	Optum	Marketscan	Medicare
Risk per 1,000 patients	9.71	9.39	27.67

10. Final Power Assessment

Date conducted: 12/01/2019

- Re-calculate power in the appropriate excel table, using the revised number of matched patients from the PS-match in Section 9. All other parameters in the table should be the same as in Section 8. If the study is to be implemented in more than one database, copy and paste excel sheet to report power for each database separately and for the pooled analysis that uses data from all databases together. Power calculations are based on the formulas from Chow et al. (2008).

- For canagliflozin vs. DPP4i
 - Pooled

Superiority Analysis		Non-inferiority Analysis	
Number of patients matched		Number of patients matched	
Reference	76,101	Reference	76,101
Exposed	76,101	Exposed	76,101
Risk per 1,000 patients	12.65	Risk per 1,000 patients	12.65
Desired HR from RCT	0.86	Assumed HR from RCT	1
Alpha (2-sided)	0.05	Alpha (2-sided)	0.05
		Non-inferiority margin	1.3
Number of events expected	1925.3553	Number of events expected	1925.3553
Power	0.911332398	Power	0.999926523

- Optum

Superiority Analysis		Non-inferiority Analysis	

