Number of patients matched		Number of patients matched	
Reference	19,532	Reference	19,532
Exposed	19,532	Exposed	19,532
Risk per 1,000 patients	7.58	Risk per 1,000 patients	7.58
Desired HR from RCT	0.86	Assumed HR from RCT	1
Alpha (2-sided)	0.05	Alpha (2-sided)	0.05
		Non-inferiority margin	1.3
Number of events expected	296.10512	Number of events expected	296.10512
Power	0.254449294	Power	0.616911596

▪ Marketscan

Superiority Analysis		Non-inferiority Analysis	
Number of patients matched		Number of patients matched	
Reference	23,168	Reference	23,168
Exposed	23,168	Exposed	23,168
Risk per 1,000 patients	7.58	Risk per 1,000 patients	7.58
Desired HR from RCT	0.86	Assumed HR from RCT	1
Alpha (2-sided)	0.05	Alpha (2-sided)	0.05
		Non-inferiority margin	1.3
Number of events expected	351.22688	Number of events expected	351.22688
Power	0.292672624	Power	0.690943556

▪ Medicare

Superiority Analysis		Non-inferiority Analysis	
Number of patients matched		Number of patients matched	
Reference	33,401	Reference	33,401
Exposed	33,401	Exposed	33,401
Risk per 1,000 patients	22.56	Risk per 1,000 patients	22.56
Desired HR from RCT	0.86	Assumed HR from RCT	1
Alpha (2-sided)	0.05	Alpha (2-sided)	0.05
		Non-inferiority margin	1.3
Number of events expected	1507.05312	Number of events expected	1507.05312
Power	0.833370249	Power	0.999133759

- For canagliflozin vs. 2nd generation SUs

- Pooled

Superiority Analysis		Non-inferiority Analysis	
Number of patients matched		Number of patients matched	
Reference	68,850	Reference	68,850
Exposed	68,850	Exposed	68,850
Risk per 1,000 patients	15.59	Risk per 1,000 patients	15.59
Desired HR from RCT	0.86	Assumed HR from RCT	1
Alpha (2-sided)	0.05	Alpha (2-sided)	0.05
		Non-inferiority margin	1.3
Number of events expected	2146.743	Number of events expected	2146.743
Power	0.937493971	Power	0.999980899

- Optum

Superiority Analysis		Non-inferiority Analysis	
Number of patients matched		Number of patients matched	
Reference	16,740	Reference	16,740
Exposed	16,740	Exposed	16,740
Risk per 1,000 patients	9.71	Risk per 1,000 patients	9.71
Desired HR from RCT	0.86	Assumed HR from RCT	1
Alpha (2-sided)	0.05	Alpha (2-sided)	0.05
		Non-inferiority margin	1.3
Number of events expected	325.0908	Number of events expected	325.0908
Power	0.274612159	Power	0.657366306

▪ Marketscan

Superiority Analysis		Non-inferiority Analysis	
Number of patients matched		Number of patients matched	
Reference	23,265	Reference	23,265
Exposed	23,265	Exposed	23,265

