Risk per 1,000 patients	9.39	Risk per 1,000 patients	9.39
Desired HR from RCT	0.86	Assumed HR from RCT	1
Alpha (2-sided)	0.05	Alpha (2-sided)	0.05
		Non-inferiority margin	1.3
Number of events expected	436.9167	Number of events expected	436.9167
Power	0.350813593	Power	0.782915462

▪ Medicare

Superiority Analysis		Non-inferiority Analysis	
Number of patients matched		Number of patients matched	
Reference	28,845	Reference	28,845
Exposed	28,845	Exposed	28,845
Risk per 1,000 patients	27.67	Risk per 1,000 patients	9.39
Desired HR from RCT	0.86	Assumed HR from RCT	1
Alpha (2-sided)	0.05	Alpha (2-sided)	0.05
		Non-inferiority margin	1.3
Number of events expected	1596.2823	Number of events expected	541.7091
Power	0.853826925	Power	0.86285876

- Stop analyses until balance and final power assessment are reviewed by primary investigators, FDA, and assigned members of advisory board. Reviewers evaluate the results of the analyses described above in Sections 9 and 10, including numbers of patients, balance in patient characteristics, follow-up time, and reasons for censoring by treatment group, as well as overall rates of outcomes and study power.

Reviewed by PI:	[name]	Date reviewed:	12/9/19
Reviewed by FDA:	[name]	Date reviewed:	12/20/19
Reasons for stopping analysis (if required):			

11. Study Confidence and Concerns

Deadline for voting on study confidence and listing concerns: 12/20/19

- If final feasibility and power analyses are reviewed and approved, proceed to the remaining protocol steps.
- All study team and advisory board members that review this protocol should at this stage provide their level of confidence for the success of the RWD study in the [Google Form](#). This form also provides space for reviewers to list any concerns that they feel may

contribute to a failure to replicate the findings of the RCT, including differences in study populations, poor measurement of study variables, or residual confounding. All responses will be kept confidential and individual-level results will only be shared with the individual respondent.

12. Register study protocol on clinicalTrials.gov

Date conducted:

- Register the study on [clinicalTrials.gov](https://clinicaltrials.gov) and upload this document.

13. Comparative Analyses

Action report name:

Date conducted:

13.1 For primary analysis:

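### Section 10: seven of the 16 risk entries do not follow from Section 9 (unweighted pooled means, and three cells holding another database's risk), so the affected event counts and powers are understated

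*Combined protocol and SAP*

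**What the plan says.** Section 9 reports the overall risk of the primary outcome by database, in the order Optum, MarketScan, Medicare. Against DPP4i the row reads "Risk per 1,000 patients 7.58 7.81 22.56"; against second-generation sulfonylureas (SU) it reads "Risk per 1,000 patients 9.71 9.39 27.67".

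Section 10 then recalculates power with the newly matched numbers. It asks the team to "copy and paste excel sheet to report power for each database separately and for the pooled analysis that uses data from all databases together" and states that "All other parameters in the table should be the same as in Section 8". There are eight tables (two comparators, each pooled and for three databases), and each has a superiority and a non-inferiority column, giving 16 risk entries. The pooled DPP4i table shows "Risk per 1,000 patients 12.65 Risk per 1,000 patients 12.65" and the pooled SU table "Risk per 1,000 patients 15.59 Risk per 1,000 patients 15.59". The MarketScan DPP4i table shows "Risk per 1,000 patients 7.58 Risk per 1,000 patients 7.58", the same row as the Optum table. The Medicare SU table has 27.67 in the superiority column and 9.39 in the non-inferiority column.

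Section 10 ends with a stop for review: "Reviewers evaluate the results of the analyses described above in Sections 9 and 10". Follow-up time and study power are among the items to be judged, and review dates are recorded for the PI and FDA.

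**The concern.** The tables contradict Section 9 and each other. A pooled analysis of all three databases must expect as many events as the three databases together, yet both pooled tables print fewer than their own database tables add up to. One Medicare SU table expects 1,596 events in one column and 542 in the other from the same matched patients. These figures went to the PI and FDA as evidence that the study was adequately powered, and Section 12 directs that the document be uploaded to a public registry. At stake is the accuracy of that record, including the headline event count for the primary comparison.

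A related sign of copying appears in Section 9. The by-arm follow-up rows for MarketScan and Medicare are identical, quartiles included, in both comparisons, while the overall rows differ.

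**Working it through.** **Inputs.** Matched patients per arm (Section 10): DPP4i 19,532 Optum, 23,168 MarketScan, 33,401 Medicare, total 76,101; SU 16,740, 23,265, 28,845, total 68,850. Risks per 1,000 (Section 9): DPP4i 7.58, 7.81, 22.56; SU 9.71, 9.39, 27.67. Hazard ratio 0.86 for superiority; margin 1.3 with a true hazard ratio of 1 for non-inferiority; two-sided alpha 0.05; 1:1 matching.

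**Formulas.**
- Expected events: E = 2 × n per arm × risk / 1000.
- Superiority power: Φ(|ln 0.86|·√E/2 − 1.96), plus the opposite tail, which matters only in the fourth decimal when E is small.
- Non-inferiority power: Φ(ln 1.3·√E/2 − 1.96).

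**Reproducing the printed figures.** With the printed risks, all 16 event counts reproduce exactly and the powers agree. Pooled DPP4i: 2 × 76,101 × 12.65/1000 = 1,925.36, power 0.9113 and 0.99993. Pooled SU: 2 × 68,850 × 15.59/1000 = 2,146.74, power 0.9375 and 0.99998. Medicare SU non-inferiority: 2 × 28,845 × 9.39/1000 = 541.71, power 0.8629. The formulas are sound; only risk inputs are in question.

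**Pooled tables (4 entries).** The printed risks are simple means: (7.58 + 7.81 + 22.56)/3 = 12.65 and (9.71 + 9.39 + 27.67)/3 = 15.59. Medicare holds 33,401/76,101 = 44% and 28,845/68,850 = 42% of matched patients. Weighting by matched patients gives:
- DPP4i: (19,532 × 7.58 + 23,168 × 7.81 + 33,401 × 22.56)/76,101 = 14.22
- SU: (16,740 × 9.71 + 23,265 × 9.39 + 28,845 × 27.67)/68,850 = 17.13

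As a check, the printed database event counts sum to 296.1 + 351.2 + 1,507.1 = 2,154.4 for DPP4i, against 1,925.4 in the pooled table. The SU superiority columns sum to 325.1 + 436.9 + 1,596.3 = 2,358.3, against 2,146.7.

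**MarketScan DPP4i (2 entries).** The table uses 7.58; Section 9 gives 7.81. The pooled 12.65 was itself built with 7.81, since 7.58 for MarketScan would give 12.57. The 7.58 is therefore a copying error and not an alternative estimate.

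**Medicare SU non-inferiority (1 entry).** The column uses 9.39, MarketScan's risk, beside 27.67 for the same 28,845 patients per arm.

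**Corrected results.**

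| Table | Events, printed → corrected | Printed count low by | Superiority power | Non-inferiority power |
|---|---|---|---|---|
| Pooled DPP4i | 1,925 → 2,165 | 11% | 0.911 → 0.939 | 0.99993 → 0.99998 |
| MarketScan DPP4i | 351 → 362 | 3% | 0.293 → 0.300 | 0.691 → 0.704 |
| Pooled SU | 2,147 → 2,358 | 9% | 0.937 → 0.956 | 0.99998 → 0.999995 |
| Medicare SU, non-inferiority only | 542 → 1,596 | 66% | not affected | 0.863 → 0.9995 |

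The count is 4 + 2 + 1 = 7 of 16. The other nine entries (DPP4i Optum and Medicare, SU Optum and MarketScan, SU Medicare superiority) match Section 9.

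**Follow-up rows in Section 9.** A quartile of two combined arms must lie between the two arms' quartiles. For DPP4i, MarketScan's overall row is 149 [72-341], but the arms' upper quartiles are 327 and 310. The overall and by-arm MarketScan rows therefore cannot all be right. Medicare's overall row, 147 [81-318], fits the same by-arm rows, which suggests that Medicare's values were pasted over MarketScan's. For SU, the shared by-arm rows are 200 [118-414] and 144 [62-327]. Both overall rows, 159 [83-358] and 172 [90-373], lie between them, so the table does not show which column was overwritten.

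**The case against.** The strongest reply is that almost nothing turns on this. Every power error is conservative, pooled power exceeds 90% before and after correction, and the primary comparison gains under three points. The one large shift concerns a single database in the secondary comparison, and Section 10 sets no power threshold by database. All of that stands. It limits the consequence but does not remove the contradictions.

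Second, seven entries come from only three distinct mistakes, because each table prints its risk twice. That is fair as a description of cause; seven is the number of cells to correct.

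Third, the Section 9 risks are dated 04/25/2019, before the full-covariate match of 11/18/2019, and the document does not say which cohort they describe. If they describe unmatched patients, the population is older: mean age of pooled DPP4i referents is 69.99 unmatched and 65.28 matched (Appendix B). True matched event counts could then differ from those above. This also stands: the correction makes Section 10 consistent with Section 9 but does not validate the risks themselves. It does not rescue the simple mean. Weighting by the unmatched Appendix B counts gives 15.88 and 19.66, even further from 12.65 and 15.59.

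Fourth, Section 10 ties other parameters to Section 8. Carrying risks forward and updating only the matched numbers is the stated method and is not disputed. Section 8 prints no risks, so Section 9 is the only documented source. Carry-forward cannot explain two risks for one cohort or a pooled total below the sum of its parts.

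On follow-up, the 341 alone does not prove that the by-arm rows, and not the overall row, are the misprint. A check of both columns against source output covers either case.

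**Conclusion.** The concern holds. Seven of 16 risk entries, in four of the eight Section 10 tables, do not follow from Section 9. The affected event counts are understated by 3% to 66% and the affected powers by up to 13.7 points. For the primary comparison the pooled event count is 11% low and superiority power should read 0.939, not 0.911.

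The conclusion assumes that Section 9 is the intended source of the risks, which nine matching entries support, and that the pooled analysis covers all matched patients, as Section 10 says. The errors are conservative: the decision to proceed is not reversed and no design element changes. The correction is still worth making, because these figures were put forward for review and are in a document meant for public posting.

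**What to change.** In Section 10:
- Compute pooled expected events as the sum over databases of matched patients times that database's Section 9 risk (equivalently, pooled risks of 14.22 for DPP4i and 17.13 for SU).
- Enter 7.81 in both columns of the MarketScan DPP4i table.
- Enter 27.67 in the Medicare SU non-inferiority column.
- Restate only the affected event counts and powers.

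In Section 9, check the by-arm follow-up rows for MarketScan and Medicare, in both comparisons, against the source output and replace whichever were overwritten.

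The cost is a spreadsheet correction of seven cells in four tables, plus a look at existing output for two databases and two comparisons. No new risk extraction and no design change are needed.

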Appendix A

#	CANVAS trial definitions	Implementation in routine care	References/Rationale	Color coding
	Trial details- Secondary indication, 4a- unintended superiority with label change		Please see the following Google Drive for further details or any missing information: https://drive.google.com/open?id=1WD618wrvwYIeaXzfLTcuKVcnnb6b-eV	Criteria
	EXPOSURE vs. COMPARISON		ICD-10 codes are not listed in this document because of excel cell size limitations and excessive number of ICD-10 codes. Full ICD-10 code lists will be available in the above Google Drive Folder (link above). ICD-9 to ICD-10 code conversions were completed using a SAS macro that implements forward/backward mapping based on the CMS ICD-9 to ICD-10 mapping: https://www.nbr.org/data/icd9-icd-10-cm-and-pcs-crosswalk-general-equivalence-mapping.html	Adequate mapping in claims
	Canagliflozin vs. placebo	Canagliflozin vs. DPP4 inhibitors (primary comparison) or vs. 2nd generation sulfonylureas (secondary)	Patorno, [name] et al. "Cardiovascular outcomes associated with canagliflozin versus other non-glipizid antidiabetic drugs: population based cohort study." BMJ 2018;360:k119 http://dx.doi.org/10.1136/bmj.k119	Intermediate mapping in claims
	PRIMARY OUTCOME			Poor mapping or cannot be measured in claims
	Major Adverse Cardiovascular Events, Including CV Death, Nonfatal Myocardial Infarction (MI), and Nonfatal Stroke HR = 0.86 (95% CI 0.75-0.97)	
Measured 1 day after drug initiation in diagnosis position specified below and inpatient care setting: Inpatient mortality/MI/Stroke --
 
For MI Any diagnosis position in inpatient care setting ICD-9 Dx 410.X (acute myocardial infarction) excluding 410.x2 (subsequent episode of care)
 
For stroke Primary diagnosis position in inpatient care setting ICD-9 discharge diagnosis: 430.xx Subarachnoid hemorrhage (SAH) 431.xx Intracerebral hemorrhage (ICH) 433.x1 Occlusion and stenosis of precerbral arteries with cerebral infarction 434.xx (excluding 434.x0) Occlusion and stenosis of cerebral arteries with cerebral infarction 436.x Acute, but ill-defined cerebrovascular events
 
Mortality- See Mortality Sheet.
	
For MI: →PPV 94% in Medicare claims data [Kiyota Y, Schneeweiss S, Glynn RJ, Cannuscio CC, Avorn J, Solomon DH. Accuracy of Medicare claims-based diagnosis of acute myocardial infarction: estimating positive predictive value on the basis of review of hospital records. American heart journal 2004;148:99-104.] →PPV 88.4% in commercially-insured population [Wahl PM, Rodgers K, Schneeweiss S, et al. Validation of claims-based diagnostic and procedure codes for cardiovascular and gastrointestinal serious adverse events in a commercially-insured population. Pharmacoepidemiology and Drug Safety 2010;19:596-603.]
 
For stroke: PPV 0.85% or higher for ischemic stroke PPV ranging from 80% to 98% for hemorrhagic stroke →[Andrade SE, Harrold LR, Tjia J, et al. A systematic review of validated methods for identifying cerebrovascular accident or transient ischemic attack using administrative data. Pharmacoepidemiology and Drug Safety 2012;21 Suppl 1:100-28.] →[Tirschwell DL, Longstreth WT, Jr. Validating administrative data in stroke research. Stroke: a journal of cerebral circulation 2002;33:2465-70.] →[Roumie CL, Mitchel E, Gideon PS, Varas-Lorenzo C, Castellsague J, Griffin MR. Validation of ICD-9 codes with a high positive predictive value for incident strokes resulting in hospitalization using Medicaid health data. Pharmacoepidemiology and drug safety 2008;17:20-6.]
	Can't be measured in claims but not important for the analysis
	INCLUSION CRITERIA			
1	Man or woman with a diagnosis of type 2 diabetes with glycated hemoglobin level $\geq 7.0\%$ to $\leq 10.5\%$ at screening and be either:	Patients with a diagnosis of T2DM (ICD-9 Dx code of 250.x0 or 250.x2) in the 180 days prior to drug initiation in any diagnosis position and inpatient or outpatient care setting.	Patorno, [name] et al. "Cardiovascular outcomes associated with canagliflozin versus other non-glipizid antidiabetic drugs: population based cohort study." BMJ 2018;360:k119 http://dx.doi.org/10.1136/bmj.k119	
	o (1) not currently on antihyperglycemic agent (AHA) therapy or o (2) on AHAmonotherapy or combination therapy with any approved class of agents: e.g., sulfonylurea, metformin, peroxisome proliferator-activated receptor gamma (PPAR γ) agonist, alpha-glucosidase inhibitor, glucagon-like peptide-1 (GLP-1) analogue, dipeptidyl peptidase-4 (DPP-4) inhibitor, or insulin.	Depending on the comparison group, we will require new-use (defined as no use 180 days prior to index date) of canagliflozin and a comparator drug	Patorno, [name] et al. "Empagliflozin and the Risk of Heart Failure Hospitalization in Routine Clinical Care: A First Analysis from the Empagliflozin Comparative Effectiveness and Safety (EMPRISE) Study." Circulation . 2019 Apr 8. doi: 10.1161/CIRCULATIONAHA.118.039177	
2	History or high risk of cardiovascular disease defined on the basis of either:			
	- Age ≥ 30 years with documented symptomatic atherosclerotic cardiovascular disease:	Age ≥ 30 years at drug initiation		
	o including stroke;	Measured 180 days prior to drug initiation in any diagnosis position and inpatient or outpatient care setting- Any stroke: ICD-9 Dx: 430.xx, 431.xx, 433.xx, 434.xx, 436.xx	Patorno, [name] et al. "Cardiovascular outcomes associated with canagliflozin versus other non-glipizid antidiabetic drugs: population based cohort study." BMJ 2018;360:k119 http://dx.doi.org/10.1136/bmj.k119	
	o or myocardial infarction (MI);	Measured 180 days prior to drug initiation in any diagnosis position and inpatient or outpatient care setting- Acute MI ICD-9 410.xx, Old MI: 412.xx	Patorno, [name] et al. "Empagliflozin and the Risk of Heart Failure Hospitalization in Routine Clinical Care: A First Analysis from the Empagliflozin Comparative Effectiveness and Safety (EMPRISE) Study." Circulation . 2019 Apr 8. doi: 10.1161/CIRCULATIONAHA.118.039177	
	o or hospital admission for unstable angina;	Measured 180 days prior to drug initiation in the inpatient care setting with ICD-9 discharge diagnosis 411.xx	Patorno, [name] et al. "Cardiovascular outcomes associated with canagliflozin versus other non-glipizid antidiabetic drugs: population based cohort study." BMJ 2018;360:k119 http://dx.doi.org/10.1136/bmj.k119	
			Patorno, [name] et al. "Empagliflozin and the Risk of Heart Failure Hospitalization in Routine Clinical Care: A First Analysis from the Empagliflozin Comparative Effectiveness and Safety (EMPRISE) Study." Circulation . 2019 Apr 8. doi: 10.1161/CIRCULATIONAHA.118.039177	

Appendix A

	
 o or coronary artery bypass graft (CABG); 	CABG: Measured 180 days prior to drug initiation in any diagnosis position and inpatient care setting - CPT-4: 33510 – 33536, 33545, 33572. OR – Measured 180 days prior to drug initiation in any diagnosis position and inpatient or outpatient care setting -ICD-9 procedure: 36.1x, 36.2x	Patorno, [name] et al. "Cardiovascular outcomes associated with canagliflozin versus other non-gliflozin antidiabetic drugs: population based cohort study." BMJ 2018;360:k119 http://dx.doi.org/10.1136/bmj.k119 Patorno, [name] et al. "Empagliflozin and the Risk of Heart Failure Hospitalization in Routine Clinical Care: A First Analysis from the Empagliflozin Comparative Effectiveness and Safety (EMPRISE) Study." Circulation . 2019 Apr 8. doi: 10.1161/CIRCULATIONAHA.118.039177
2a	
 o or percutaneous coronary intervention (PCI; with or without stenting); 	PTCA: Measured 180 days prior to drug initiation in any procedure position and inpatient care setting - CPT-4: 92973, 92982, 92984, 92995, 92996, 92920 – 92921, 92924 – 92925, 92937, 92938, 92941, 92943, 92944 OR – Measured 180 days prior to drug initiation in any procedure position and inpatient or outpatient care setting -ICD-9 procedure: 00.66, 36.01, 36.02, 36.03, 36.05, 36.09 Stenting: Measured 180 days prior to drug initiation in any procedure position and inpatient care setting - CPT-4: 92980, 92981, 92928 – 92929, 92933 - 92934 OR – Measured 180 days prior to drug initiation in any procedure position and inpatient or outpatient care setting -ICD-9 procedure: 36.06, 36.07	Patorno, [name] et al. "Cardiovascular outcomes associated with canagliflozin versus other non-gliflozin antidiabetic drugs: population based cohort study." BMJ 2018;360:k119 http://dx.doi.org/10.1136/bmj.k119 Patorno, [name] et al. "Empagliflozin and the Risk of Heart Failure Hospitalization in Routine Clinical Care: A First Analysis from the Empagliflozin Comparative Effectiveness and Safety (EMPRISE) Study." Circulation . 2019 Apr 8. doi: 10.1161/CIRCULATIONAHA.118.039177
	
 o or peripheral revascularization (angioplasty or surgery); 	Measured 180 days prior to drug initiation in any diagnosis position and inpatient or outpatient care setting -ICD-9 39.25, 39.50, 39.99.	Patorno, [name] et al. "Cardiovascular outcomes associated with canagliflozin versus other non-gliflozin antidiabetic drugs: population based cohort study." BMJ 2018;360:k119 http://dx.doi.org/10.1136/bmj.k119 Patorno, [name] et al. "Empagliflozin and the Risk of Heart Failure Hospitalization in Routine Clinical Care: A First Analysis from the Empagliflozin Comparative Effectiveness and Safety (EMPRISE) Study." Circulation . 2019 Apr 8. doi: 10.1161/CIRCULATIONAHA.118.039177
	
 o or symptomatic with documented hemodynamically-significant carotid or peripheral vascular disease; 	Measured 180 days prior to drug initiation in any diagnosis position and inpatient or outpatient care setting -ICD9 diagnosis: 440.20 – 440.24, 440.29 – 440.32, 440.3, 440.4, 443.9	Patorno, [name] et al. "Cardiovascular outcomes associated with canagliflozin versus other non-gliflozin antidiabetic drugs: population based cohort study." BMJ 2018;360:k119 http://dx.doi.org/10.1136/bmj.k119 Patorno, [name] et al. "Empagliflozin and the Risk of Heart Failure Hospitalization in Routine Clinical Care: A First Analysis from the Empagliflozin Comparative Effectiveness and Safety (EMPRISE) Study." Circulation . 2019 Apr 8. doi: 10.1161/CIRCULATIONAHA.118.039177
	
 o or amputation secondary to vascular disease. 	Measured 180 days prior to drug initiation in any diagnosis position and inpatient or outpatient care setting - Lower extremity amputation ICD-9 diagnosis: V49.7x ICD-9 procedure: 84.10-84.18 CPT: 27590, 27591, 27592, 27880, 27881, 27882, 27884, 27886, 27888, 27889, 28800, 28805, 28810, 28820, 28825	Patorno, [name] et al. "Cardiovascular outcomes associated with canagliflozin versus other non-gliflozin antidiabetic drugs: population based cohort study." BMJ 2018;360:k119 http://dx.doi.org/10.1136/bmj.k119 Patorno, [name] et al. "Empagliflozin and the Risk of Heart Failure Hospitalization in Routine Clinical Care: A First Analysis from the Empagliflozin Comparative Effectiveness and Safety (EMPRISE) Study." Circulation . 2019 Apr 8. doi: 10.1161/CIRCULATIONAHA.118.039177
– Age ≥50 years with 2 or more of the following risk factors determined at the screening visit:		Age ≥50 years at drug initiation	
	
 o duration of type 2 diabetes of 10 years or more 	N/A	We can't capture diabetes duration but will match on number of antidiabetic drugs during baseline
	
 o or systolic blood pressure >140 mmHg (average of 3 readings) recorded at the screening visit 	Measured 180 days prior to drug initiation in any diagnosis position and inpatient or outpatient care setting - Hypertension ICD-9 codes 401.x – 405.x	Patorno, [name] et al. "Cardiovascular outcomes associated with canagliflozin versus other non-gliflozin antidiabetic drugs: population based cohort study." BMJ 2018;360:k119 http://dx.doi.org/10.1136/bmj.k119 Patorno, [name] et al. "Empagliflozin and the Risk of Heart Failure Hospitalization in Routine Clinical Care: A First Analysis from the Empagliflozin Comparative Effectiveness and Safety (EMPRISE) Study." Circulation . 2019 Apr 8. doi: 10.1161/CIRCULATIONAHA.118.039177
2b	
 o or while the subject is on at least one blood pressure-lowering treatment 	Dispensing of at least one of the following medications in the 180 days prior to drug initiation: ACE inhibitor Benazepril, captopril, enalapril, fosinopril, lisinopril, moexipril, perindopril, quinapril, ramipril, trandolapril ARB Ailsartan, candesartan, eprosartan, irbesartan, losartan, olmesartan, telmisartan, valsartan Beta blocker Acebutolol, atenolol, betaxolol, bisoprolol, carteolol, carvedilol, esmolol, labetalol, metoprolol tartrate, metoprolol succinate, propranolol, pindolol, nadolol, nebivolol, sotalol, timolol Calcium channel blocker Diltiazem, mibepradil, verapamil, amlodipine, clevidipine, bepridil, felodipine, isradipine, nicardipine, nifedipine, nimodipine, nisoldipine Loop diuretics Furosemide, bumetanide, torsemide, ethacrynic acid Other diuretics Amiloride, eplerenone, spironolactone, triamterene Other hypertension drugs Doxazosin, eplerenone, prazosin, terazosin, clonidine, guanabenz, guanadrel, guanethidine, guanfacine, hydralazine, methyldopa, metyrosine, reserpine, minoxidil, aliskiren	Patorno, [name] et al. "Cardiovascular outcomes associated with canagliflozin versus other non-gliflozin antidiabetic drugs: population based cohort study." BMJ 2018;360:k119 http://dx.doi.org/10.1136/bmj.k119 Patorno, [name] et al. "Empagliflozin and the Risk of Heart Failure Hospitalization in Routine Clinical Care: A First Analysis from the Empagliflozin Comparative Effectiveness and Safety (EMPRISE) Study." Circulation . 2019 Apr 8. doi: 10.1161/CIRCULATIONAHA.118.039177

